4. The patient will have standing radiographs of the affected knee.

Evaluation at the time of surgery:

At the time of surgery, the patient will be randomized to treatment with either an arthroscopic partial meniscectomy or arthroscopic lavage. Randomization will be done by opening a sealed envelope in the operating room prior to the procedure. To ensure balanced numbers in the two surgical conditions, especially at the time of the interim look, randomization will be done by permuted blocks of size 10, thereby ensuring 5 patients in each group at every increment of 10 enrollees.

Upon initiation of the surgery, a sample of synovial tissue and synovial fluid will be obtained for biochemical analysis. During the operation, the status of the knee joint will be documented. This will include classifying the degree of chondromalacia according to the Outerbridge classification in all three compartments of the knee, and documenting the geometry and pattern of meniscus tear type. Video and photographs will be taken to assist with this documentation and will be stored in a secure manner.

During the operation, the meniscus will be carefully probed. If a large unstable flap of tissue can be displaced into the articulation (such as a bucket handle tear) this torn fragment will be debrided regardless of the result of randomization. This will be done as it is widely believed that it is inappropriate to leave such an unstable tear untreated. Any other tear types that do not result in an unstable flap that can be displaced into the articulation will be either retained or debrided, depending on the result of randomization.

All postoperative contact from this point forward will be made by study personnel who were not involved in the surgery and who do not have knowledge of the randomization result.

At 2 weeks and 6 weeks:

The patient will have regularly scheduled clinic visits at 2 and 6 weeks that are not a part of the study but are just a part of the routine postoperative care of knee arthroscopy patients. Postoperative care as deemed necessary by the treating physician will be provided and could include pain and/or anti-inflammatory medications. Physical therapy is rarely needed. All provided treatments will be recorded in the chart.

Evaluation at 3 months:

1. The patient will fill out WOMET and WOMAC surveys.
2. The patient will undergo gait analysis.
3. The patient will have an MRI of the knee

Evaluation at 6 months:

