Hypothesis 1a: The 12 month WOMAC score will be our primary outcome measure for this aim and the endpoint for this power analysis. The WOMAC is a validated osteoarthritis outcome tool that is widely used to assess the severity of pain, stiffness, and function due to osteoarthritis. A 20% improvement in the total WOMAC score is considered to be clinically important (Kirkley et al., 2008). In a preliminary study, we evaluated a cohort of 45 patients undergoing arthroscopy and meniscectomy at our institution (Mirza et al., 2010). We found a mean preoperative WOMAC score of 1296 with a standard deviation of 392. Twenty percent of the mean baseline score of 1296 is 260.

To ensure patient safety, we are incorporating in our analysis an interim look at the results by the DSMB to ensure that one group does not have dramatically superior results to another group. In addition, the DSMB will assess subject attrition rates by group and adverse events.

This will take place after 25% of the total planned number of subjects complete the study. This analysis will include assessment of drop-out rates and adverse events as well.

Setting the experiment-wide alpha at 0.05 and power at 80%, sample sizes of 37 and 37 achieve 81% power to detect a difference of 260 between the group means with standard deviations of 392 and 392 at a significance level (alpha) of 0.05 using a two-sided independent sample t-test. These results assume that 2 sequential tests are made using the O'Brien-Fleming spending function to determine the test boundaries. The interim look will thus take place when the first 20 subjects (25% of the total 74) complete the 12 month assessment. The analysis assumes that we will stop the trial if either condition is superior. The critical t-value will at the interim look will be +/- 4.3326. If the trial continues, the final analysis will use a critical t-value of 1.96. Sensitivity analyses will be conducted with t-tests on the baseline-to-12-month change scores.

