74 subjects will thus be needed to complete the trial. Over a one year period we will expect to have a 10% lost to follow-up rate. We will thus plan to enroll 82 subjects into the study. With a 70% recruitment rate we will need to have 117 candidate patients for this study. In calendar year 2011, we performed 66 arthroscopic meniscectomies at our facility. Assuming that 70% of these cases involved stable degenerative tears, we would have 46 candidate patients per year. It would thus take us approximately 2.5 years to recruit enough patients for the study if we were to operate at last year's rate. We presently have approximately 100 patients for knee arthroscopy on our waiting list for surgery, which makes it likely that we could accomplish this goal more rapidly.

Hypothesis 1b: Should we fail to find a difference in 12 month WOMAC scores, we will test the hypothesis that the WOMAC scores in the arthroscopy and lavage condition are at least as good as (non-inferiority) the meniscectomy by setting "d" the largest difference in WOMAC scores which we consider to be clinically meaningless to 15% of baseline, or 194 points. We will then calculate 90% confidence limits for the difference in means for the two groups and determine whether these confidence limits lie within the -194 to 194 point interval. Since there is no danger to patients if this hypothesis is found to be true, this hypothesis will not be subject to an interim analysis. We will assume that the standard deviation of the means is 392. With these numbers, the sample size of 74 and alpha = .10 and yields power = .80.

Aim 2: *To test the functional effect of arthroscopic meniscectomy in the setting of a degenerative meniscus tear.*

Hypothesis 2: Subjects randomized to arthroscopy and meniscectomy will have greater changes in tibio-femoral rotation, knee adduction moment, and knee flexion moment at 12 months following surgery when compared to subjects randomized to arthroscopy and lavage.

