Calculations were performed to estimate the necessary sample size for the endpoints of Aim 2 of changes in tibio-femoral rotation, knee adduction moment, and knee flexion moment. In order to keep the family-wise error rate at .05, each comparison will be made with an independent sample t-test with alpha = 0.0167. To reject the null hypothesis that changes in tibio-femoral rotation will not differ between the intervention (meniscectomized) knees and control (non-meniscectomized knees), data from a similar study performed in our laboratory evaluating tibial rotation using the same techniques between meniscectomized knees and intact knees was used (Netravali et al., 2010). In that study, we found a 3.2 degree difference in tibio-femoral rotation in meniscectomized knees when compared to intact contralateral knees using a t-test. The standard deviation of the measurements in the meniscectomized knees was 3.8 degrees. Thus, to detect a difference of 3.2 degrees tibio-femoral rotation in the meniscectomized group

versus no change in the intact group, with an alpha of 0.0167 and 74 total patients, power of 87% will be achieved.

In addition, we would be interested to detect a change in peak adduction moment of about 10% of baseline value. This corresponds to a change of 0.35%BW*ht (Netravali et al., 2010). Prior work looking at changes in knee adduction moment with intervention find a standard deviation of the difference in peak adduction moment with the intervention to be 0.35%BW*ht. With an alpha of 0.0167 and 74 total patients, power of 94% will be achieved.

Finally, we are interested in detecting a change in peak flexion moment of about 10% baseline value. This corresponds to a change of 0.3%BW*ht (Netravali et al., 2010). Assuming a standard deviation of the flexion moment of approximately 0.35%BW*ht. With an alpha of 0.0167 and 74 total patients, power of 89% will be achieved.

Missing Data:

All analyses will be on the intent-to-treat sample. To address missing data at 1 year (and other time points), we will use a multiple imputation strategy that minimizes potential attrition bias. Ten datasets will be imputed with draws from the theoretical complete data distribution using the Multivariate Imputation by Chained Equations (MICE) program implemented in the R statistical language. All analyses with these data will be conducted on the imputed datasets and combined to yield the final parameter estimates and inferences.

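### Aim 2 tests three gait endpoints at a fixed 0.0167 each; this is valid, but Holm's step-down procedure would hold the same 0.05 family-wise error with at least as much power.

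*Combined protocol and SAP*

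**What the plan says.** Under Statistical Analysis, Aim 2, Hypothesis 2 predicts that the meniscectomy arm will show "greater changes in tibio-femoral rotation, knee adduction moment, and knee flexion moment at 12 months following surgery" than the lavage arm. The sample-size text for this aim gives the error goal, "In order to keep the family-wise error rate at .05", and the rule that serves it: "each comparison will be made with an independent sample t-test with alpha = 0.0167". The plan does not name Bonferroni, but 0.05/3 = 0.0167. It describes no step-down, hierarchical or other sequential procedure for Aim 2.

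Each endpoint is powered at that level with 74 patients. The stated powers are 87% for tibio-femoral rotation, 94% for peak adduction moment and 89% for peak flexion moment.

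**The concern.** Under the fixed split, every endpoint must reach 0.0167 even after another endpoint has already been rejected. Once one null hypothesis is rejected, at most two can still be true, so the full three-way split is stricter than the 0.05 goal requires. Holm's procedure uses this. It tests the smallest p-value at 0.0167, the next at 0.025 and the largest at 0.05, and stops at the first failure.

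What is at stake is power on the second and third gait endpoints, in a single-centre trial planned for 74 completers. The validity of any Aim 2 conclusion is not in question.

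**Working it through.** **Inputs from the plan**
- Family-wise error 0.05 and three endpoints (Aim 2).
- 37 per arm. Hypothesis 1a states "sample sizes of 37 and 37 achieve 81% power", and the randomization text under Evaluation at the time of surgery gives equal allocation.
- Rotation: difference 3.2 degrees, SD 3.8, so d = 3.2/3.8 = 0.842.
- Adduction moment: difference 0.35, SD 0.35, so d = 1.000.
- Flexion moment: difference 0.30, SD 0.35, so d = 0.857.

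**Assumptions**
- Two-sided tests. Aim 2 does not state sidedness; Hypothesis 1a does ("using a two-sided independent sample t-test"). Two-sided testing reproduces the stated powers for rotation and flexion. One-sided testing would give about 92.5% and 93.3%.
- A common correlation of 0, 0.3 or 0.6 between endpoints. The documents give none.

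**Step 1: reproduce the plan's power.** For a two-sample t-test with 72 degrees of freedom, the noncentrality is d × √(37/2) = d × 4.301. That gives 3.62, 4.30 and 3.69. The critical value at 0.0167 is 2.45.

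| Endpoint | Stated | Recomputed at 0.0167 |
|---|---|---|
| Rotation | 87% | 87.6% |
| Adduction | 94% | 96.6% |
| Flexion | 89% | 88.9% |

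Rotation and flexion reproduce. Adduction recomputes to about 97%, so the stated figure is conservative. To arrive at 94% would take an SD of about 0.374, a difference of about 0.328, or about 33 per arm. This does not affect the comparison below.

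**Step 2: chance of all three, independent endpoints.** Fixed split: 0.876 × 0.966 × 0.889 = 0.752. Holm cannot exceed the product of the powers at 0.05, which is 0.947 × 0.989 × 0.953 = 0.892. Simulation gives 0.890.

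**Step 3: simulation** (at least 100,000 trials per scenario, 37 per arm). Power is shown as fixed split → Holm.

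All three planned effects real:

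| Correlation | Rotation | Adduction | Flexion | All three |
|---|---|---|---|---|
| 0 | 87.7 → 94.2% | 96.5 → 98.6% | 88.9 → 94.9% | 75.1 → 89.0% |
| 0.3 | 87.7 → 93.8% | 96.6 → 98.3% | 89.0 → 94.6% | 77.5 → 89.6% |
| 0.6 | 87.7 → 93.5% | 96.6 → 97.8% | 88.8 → 93.9% | 80.4 → 90.7% |

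Fewer real effects:
- Rotation and flexion real, adduction null, correlation 0: rotation 87.6 → 90.3%, flexion 88.9 → 91.4%. False rejection of adduction rises from 1.7 to 4.6%.
- Only rotation real: rotation gains about 0.1 point (for example 87.7 → 87.8%).
- At least one rejection: identical under both rules in every scenario, because both compare the smallest p-value with 0.0167.

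**Step 4: error control.** With no real effects, both rules have the same family-wise error. With independent endpoints it is 1 − (1 − 0.05/3)³ = 0.049, and it falls to about 0.042 at correlation 0.6. In no simulated trial did the fixed split reject a hypothesis that Holm did not.

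**The case against.** The strongest reply is that nothing here is wrong. The plan names its error goal, pre-specifies a rule that meets it, and powers each endpoint at that level to at least 87%, above the 80% set for Aim 1. That stands, and it limits the point to an efficiency gain.

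A reader might also infer three stronger things that the documents do not support.

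- **That power is lost on all three endpoints whatever the truth.** The gain arises only after another endpoint is rejected, and the large figures need all three effects to be real at planned size. For adduction and flexion, the plan gives changes of about 10% of baseline that the team would like to detect, not effects it has seen in this comparison. The rotation effect comes from meniscectomized against intact contralateral knees: "we found a 3.2 degree difference in tibio-femoral rotation in meniscectomized knees". The section on mechanisms of osteoarthritis progression treats no kinematic change from resection as a real possibility. The all-three scenario is therefore the most favourable one.
- **That confirming all three is what counts.** Hypothesis 2 lists three changes, but no text says Aim 2 succeeds only if all are significant, and family-wise control over separate comparisons suggests separate claims. If all three were required, each could be tested at 0.05 with no split, and power would be about 89-91%, equal to Holm or slightly above it. The rise from 75-80% to 89-91% describes the size of the gain; it is not evidence of a failed success criterion.
- **That the fixed split buys nothing in error control.** Both rules respect the 0.05 family-wise limit, but the fixed split keeps the error on a single null endpoint lower (1.7% against 4.6% in the example above). The plan's stated goal does not ask for this, but it is a real trade.

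**Conclusion.** The point holds as a cheap improvement to a valid rule. Holm serves the plan's own error goal equally well and can never reject less. That much needs no assumption about correlation or effect size.

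The size of the gain does depend on assumptions: the plan's effects and SDs, 37 per arm, two-sided tests, and correlations of 0 to 0.6. It is about 1-7 points per endpoint and 10-14 points for all three if every effect is real. With two real effects (rotation and flexion) it is 2-3 points each. With one real effect it is negligible, and it is always zero for the chance of at least one finding.

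**What to change.** Before unblinded analysis, replace the fixed 0.0167 in Aim 2 with a statement that the three 12-month gait endpoints will be tested by Holm's step-down procedure at a family-wise two-sided 0.05. The procedure would be applied to the p-values obtained after the planned multiple imputation has been combined. Stating the sidedness in the same sentence removes an ambiguity.

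Keep the present power figures, labelled as lower bounds from the fixed split, and either correct the 94% for adduction to about 97% or explain its inputs.

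The cost is one sentence. Sample size, data collection and the t-tests do not change. Simultaneous confidence intervals that match Holm are less simple than those for the fixed split, although the plan specifies none for Aim 2. The team should also accept knowingly the higher false-rejection rate on a single null endpoint when the other effects are real.

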Imaging of muscle cross sectional area: Muscle cross sectional area measurement can provide additional information regarding the functional consequences of meniscectomy. We will image the thigh of patients at enrollment, and at two-year follow up to determine if patients undergoing meniscectomy vs. lavage have greater changes in muscle cross sectional area. Images will be obtained using a rapid axial thigh scan with IDEAL fat/water separation using a 3D spoiled gradient echo sequence. The data will have 1 mm in-plane resolution and 5 mm slice thickness. Acquisition time will be approximately 2 minutes. Muscle cross sectional area will then be determined as previously described {Walton 1997}.

Research Design and Methods

In this study we propose a prospective, randomized, blinded, and controlled clinical trial of arthroscopic meniscectomy in patients between the ages of 45 and 70 with degenerative meniscus tears.

Patient Selection:

Subjects will be recruited from the orthopedic clinic at the VA Palo Alto Healthcare System. Eligible subjects will meet the following inclusion criteria:

1. Age between 45 and 70 years
2. Degenerative meniscus tear as seen by a standard clinical MRI scan
3. A complaint of “mechanical symptoms” which would include popping, catching, or locking of the knee
4. Persistent symptoms for a minimum of three months despite conservative management including anti-inflammatory medications and physical therapy
5. Patient is enrolled for arthroscopic meniscectomy
6. The subject agrees to study follow-up schedule and signs informed consent.

The following exclusion criteria will be enforced:

1. Radiographic osteoarthritis of the knee in any compartment that is greater than KL grade 2
2. Prior knee arthroscopy within two years of study enrollment
3. Unable to have an MRI scan
4. Does not agree to participate

General Study Plan:

Patients who satisfy the inclusion and exclusion criteria and are scheduled for arthroscopic meniscectomy will be approached during their preoperative visit to participate in the study. They will be enrolled when they give informed consent.

Preoperative study related evaluation:

Prior to undergoing surgery, the patient will have the following evaluations:

1. The patient will fill out the WOMET (Kirkley et al., 2007) and WOMAC (Bellamy et al., 1988) surveys.
2. The patient will undergo a gait analysis
3. The patient will have MRI of the knee and thigh.

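### Aim 2 compares raw 12-month changes in gait by t-test although preoperative gait is measured, giving up about 7 to 8 points of power on rotation and flexion moment if the baseline correlation is 0.5

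*Combined protocol and SAP*

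**What the plan says.** Under Statistical Analysis, Aim 2, Hypothesis 2 states that patients randomized to meniscectomy "will have greater changes in tibio-femoral rotation, knee adduction moment, and knee flexion moment at 12 months following surgery" than patients randomized to lavage. The sample-size text that follows describes the "endpoints of Aim 2 of changes in tibio-femoral rotation, knee adduction moment, and knee flexion moment" and fixes the analysis: "each comparison will be made with an independent sample t-test with alpha = 0.0167". It then claims power of 87% for rotation, 94% for adduction moment and 89% for flexion moment with 74 patients.

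The baseline value is collected. The list of preoperative evaluations includes "The patient will undergo a gait analysis", and gait analysis is repeated at 3 and 12 months.

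No part of the plan adjusts the gait comparison for baseline gait:

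- The secondary adjusted analyses in the Randomization subsection name symptom duration, chondromalacia grade, Kellgren-Lawrence grade and depression as the covariates.
- The change-score sensitivity analysis under Hypothesis 1a is for WOMAC.
- The Missing Data subsection specifies multiple imputation, which does not adjust for baseline.

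**The concern.** Subtracting the baseline is the same as fixing its regression coefficient at 1. When baseline and follow-up are imperfectly correlated and have similar SDs, the best coefficient is below 1, and forcing it to 1 adds noise to the treatment comparison. A chance imbalance in preoperative gait also stays in the estimate through regression to the mean: an arm that starts high by chance tends to show a larger fall.

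Aim 2 is the trial's only powered evidence on whether resection alters knee mechanics. The background section says that finding the kinematic change only after meniscectomy would point to the operation, rather than the tear, as the cause of later osteoarthritis. A null result would therefore be interpreted. Each test is already held to 0.0167, so avoidable noise raises the chance of a false null.

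The planning effect may also be optimistic. The 3.2 degrees for rotation came from meniscectomized knees against healthy contralateral knees, whereas this trial compares resected with unresected torn knees. If the true contrast is smaller, the efficiency loss costs more power.

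**Working it through.** **Inputs from the plan.** There are 37 completers per arm ("sample sizes of 37 and 37 achieve 81% power"; 82 are enrolled to leave 74, so 37 is already net of dropout). Alpha is 0.05/3 per comparison. A two-sided test is stated only for Aim 1, but it is what reproduces the Aim 2 figures for rotation and flexion moment. Effects and SDs are 3.2 and 3.8 degrees for rotation, 0.35 and 0.35 %BW*ht for adduction moment, and 0.30 and 0.35 %BW*ht for flexion moment.

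**Inputs not in the plan.** The baseline-to-12-month correlation (rho) and the ratio of the 12-month SD to the baseline SD are assumptions. The base case is rho = 0.5 and equal SDs.

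**Step 1: reproduce the plan.** Two-sample t-test, noncentral t, 72 df, noncentrality = (effect/SD) × √(37/2):

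- Rotation: 3.2/3.8 = 0.842; × 4.301 = 3.62; power 87.6% (stated 87%).
- Flexion moment: 0.30/0.35 = 0.857; × 4.301 = 3.69; power 88.9% (stated 89%).
- Adduction moment: 0.35/0.35 = 1.000; × 4.301 = 4.30; power 96.6% (stated 94%). The stated figure is a little below what its own inputs give. This is a separate discrepancy in the conservative direction and does not affect the point.

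**Step 2: compare the variances.** With baseline SD s0 and 12-month SD s1:

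- Change score: s0² + s1² − 2·rho·s0·s1.
- ANCOVA residual: s1²(1 − rho²).
- Difference: (s0 − rho·s1)², which is never negative.

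With s0 = s1 the variance ratio is (1 − rho²)/(2(1 − rho)) = (1 + rho)/2. At rho = 0.5 it is 0.75, so the SD is multiplied by √0.75 = 0.866. Equivalently, about 75% of the patients would give the same power.

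**Step 3: power with ANCOVA, 71 df, rho = 0.5** (gains are taken before rounding):

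| Endpoint | t-test on change | ANCOVA | Gain (points) |
|---|---|---|---|
| Rotation | 87.6% | 95.6% | 8.0 |
| Flexion moment | 88.9% | 96.2% | 7.4 |
| Adduction moment | 96.6% | 99.3% | 2.8 |

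A simulation of 20,000 trials per endpoint agrees: 87.8% to 95.3%, 88.6% to 95.7% and 96.7% to 99.2%.

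**Step 4: vary rho, under both readings of the SD.** The plan words the adduction SD as that of a difference, but the rotation and flexion SDs as those of a measurement. If they are SDs of change, the ANCOVA SD is SD × √((1 + rho)/2). If they are SDs of a level, the change-score SD is SD × √(2(1 − rho)) and the ANCOVA SD is SD × √(1 − rho²).

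| rho | Rotation, SD of change | Flexion, SD of change | Rotation, SD of level | Flexion, SD of level |
|---|---|---|---|---|
| 0.3 | 87.6% to 97.8% (+10.2) | 88.9% to 98.1% (+9.3) | 72.8% to 90.8% (+18.0) | 74.5% to 91.8% (+17.3) |
| 0.5 | 87.6% to 95.6% (+8.0) | 88.9% to 96.2% (+7.4) | 87.6% to 95.6% (+8.0) | 88.9% to 96.2% (+7.4) |
| 0.7 | 87.6% to 92.7% (+5.1) | 88.9% to 93.6% (+4.8) | 98.6% to 99.5% (+0.9) | 98.8% to 99.6% (+0.8) |
| 0.8 | 87.6% to 91.1% (+3.5) | 88.9% to 92.1% (+3.3) | below +0.1 | below +0.1 |

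The readings coincide at rho = 0.5 because 2(1 − rho) = 1 there.

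**Step 5: vary the SD ratio** (rotation, SD of change, rho = 0.5). The gain is 11.3 points if the 12-month SD is 0.8 times the baseline SD, 8.0 at ratio 1.0, 4.4 at 1.2 and 3.1 at 1.3. At ratio 1.2 it falls to 1.2 points at rho 0.7 and 0.1 at rho 0.8.

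**Step 6: a smaller true effect.** At 75% of the planned effect (an illustration) with rho = 0.5 and equal SDs, rotation power is 60.6% by t-test and 75.2% by ANCOVA; flexion moment is 62.4% and 76.9%.

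**The case against.** The strongest reply is that nothing here is wrong. Under randomization the change-score t-test is unbiased and holds its error rate, it matches a hypothesis worded in terms of change, and all three stated powers exceed the trial's 80% target. Aim 1, not Aim 2, set the sample size. This stands: the point is about efficiency, not validity.

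The size is also uncertain. The documents give neither a gait correlation nor an SD ratio. On the reading closest to the text for rotation and flexion (SD of a measurement), the gain is under 1 point at rho 0.7. If resected knees respond unevenly and the 12-month SD is larger than at baseline, the best coefficient moves towards 1 and the gain falls below 5 points even at rho 0.5. This stands too, and it is why the 7 to 8 points must be read as conditional. The uncertainty runs both ways, though: a lower correlation or a smaller 12-month SD makes the gain larger. Apart from one degree of freedom, ANCOVA is not less precise in any of these cases.

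It can also be said that the Randomization subsection already plans covariate adjustment and propensity weights built from pre-treatment data. Baseline gait is such a variable, but it is not among the covariates named, and those analyses are secondary. Finally, a general sentence on baseline adjustment could cover WOMAC as well. Aim 2 has different endpoints and its own stated test, so it still needs its own wording.

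**Conclusion.** The point holds. The Aim 2 tests ignore the regression on a baseline value that the trial collects for each endpoint. At rho 0.5 with equal SDs this costs 8.0 points of power for rotation, 7.4 for flexion moment and 2.8 for adduction moment. With equal SDs, the rotation loss is at least 5 points for rho up to about 0.7 if the stated SD is of change, or up to about 0.55 if it is of a level. It becomes negligible at high correlation on the level reading. The planned test remains valid and its nominal power is adequate, so this is an improvement that should be made, not an error that invalidates the aim.

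**What to change.** In the Aim 2 text, replace the t-tests with a linear regression for each endpoint of the 12-month gait value on arm and the preoperative value of the same measure, fitted in each imputed dataset and combined as already planned. Using the change as the outcome gives the same treatment estimate, provided baseline is in the model. Keep 0.0167 per comparison, and report the unadjusted change-score t-test as a sensitivity analysis. It would also help to state whether 3.8 degrees and 0.35 %BW*ht (flexion) are SDs of change or of a single measurement.

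The cost is one sentence in the SAP and one degree of freedom per model, with no new data, visits or patients. The effect is then reported as baseline-adjusted. The change should be made before any outcome data are seen by arm.

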This study shows that we have the ability to identify changes in knee kinematics and kinetics after meniscectomy using our current gait analysis techniques. A key piece of information that is missing, however, is the kinematics of the knee with the meniscus tear that has not been debrided. Though we have seen these kinematic changes in knees during gait after meniscectomy, it is not clear whether these changes were actually caused by the meniscectomy or by the injury/meniscus tear itself. This is an important distinction as it begins to probe the etiology of post meniscectomy osteoarthritis. If we find that these kinematic changes in knees during gait are present only after meniscectomy, we would have reason to believe that post-meniscectomy osteoarthritis is a result of the surgical intervention itself (partial meniscectomy) rather than just due to the meniscus tear.

Relation between knee walking kinematics and spatial cartilage thickness distribution in the knee

We have done previous work relating the kinematics of walking on the spatial distribution of articular cartilage thickness in the knee (Koo et al., 2011). Gait data and knee MR images were obtained from 17 healthy volunteers (age 33.2 ± 9.8 years). Cartilage thickness maps were created for the femoral and tibial cartilage. Locations of thickest cartilage in the medial and lateral compartments in the femur and tibia were identified using a numerical method. The flexion-extension (FE) angle associated with the cartilage contact regions on the femur, and the anterior-posterior (AP) translation and internal-external (IE) rotation associated with the cartilage contact regions on the tibia at the heel strike of walking were tested for correlation with the locations of thickest cartilage. The locations of the thickest cartilage had relatively large variation (SD, 8.9°) and was significantly associated with the FE angle at heel strike only in the medial femoral condyle ($R(2)=0.41$, $p<0.01$).

[figure not shown]

Fig. 3. (A) Primary (FE) and secondary (AP and IE) kinematics in the knee during walking, (B) femoral contact location (dotted arrow) predicted from FE angle (solid arrow), and (C) tibial contact location (solid line) predicted from AP translation and IE rotation.

[figure not shown]

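### The 87% power for tibio-femoral rotation is correct arithmetic on inputs from a different comparison, so it is not supported as the power of the planned test

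*Combined protocol and SAP*

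**What the plan says.** Hypothesis 2 (Statistical Analysis, Aim 2) predicts for the meniscectomy arm "greater changes in tibio-femoral rotation, knee adduction moment, and knee flexion moment at 12 months following surgery"; the comparator is the lavage arm. Each of the three endpoints is tested by an independent-sample t-test at alpha 0.0167.

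The lavage knees are torn knees. Every patient is enrolled with a degenerative tear, and under Evaluation at the time of surgery, tears without a displaceable unstable flap "will be either retained or debrided, depending on the result of randomization". A baseline exists, because the preoperative evaluation includes gait: "The patient will undergo a gait analysis".

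The rotation power rests on an earlier study from the same laboratory: "we found a 3.2 degree difference in tibio-femoral rotation in meniscectomized knees when compared to intact contralateral knees using a t-test". On its spread the plan says: "The standard deviation of the measurements in the meniscectomized knees was 3.8 degrees". It concludes: "versus no change in the intact group, with an alpha of 0.0167 and 74 total patients, power of 87% will be achieved".

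The section Effects of Meniscectomy on Gait and Functional Measures describes that study as ten patients, with the healthy opposite knee as reference. Of the kinematic differences found there it says: "it is not clear whether these changes were actually caused by the meniscectomy or by the injury/meniscus tear itself".

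**The concern.** Two inputs do not match the planned test.

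**Effect.** A resected knee compared with a healthy knee shows whatever the tear did plus whatever the resection did. Both trial arms carry the tear at baseline, so only the resection part can appear as a between-arm difference in change. Using the full 3.2 degrees assumes that the tear contributes nothing. The section Understanding mechanisms of osteoarthritis progression allows the opposite extreme, in which the whole shift is present before surgery, and says that Aim 2 is meant to settle this. The power statement therefore presumes one answer to the question being asked.

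**SD.** The endpoint is a change, but 3.8 degrees describes measurements in operated knees. For the adduction moment the same section does use the SD of a difference.

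At stake is how a null rotation result is read. The protocol intends to reason from this comparison to the cause of post-meniscectomy osteoarthritis. A null result labelled as coming from an 87%-powered test would look more reassuring about resection than the inputs justify.

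**Working it through.** **Inputs.** 74 patients, 37 per arm (the 1:1 split in the Aim 1 power paragraph); alpha 0.0167; difference 3.2 degrees; SD 3.8 degrees (all Aim 2). Two-sided testing is stated for Aim 1 only and is assumed here. The correlation r between baseline and 12-month rotation, and the share of the 3.2 degrees due to resection, are not in the documents and are varied as assumptions.

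**1. Reproduce the stated figure.** Noncentrality = (3.2/3.8) × √(37/2) = 0.842 × 4.301 = 3.62. The two-sided critical t at 0.0167 with 72 df is 2.45. Power from the noncentral t is 87.6%, which matches 87%. A one-sided test would give 92.5%, so two-sided is the variant that fits.

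**2. What the trial's contrast contains.** Let T be the shift due to the tear and R the shift due to resection, taken as additive. The source study estimates T + R = 3.2. In the trial the meniscectomy arm changes by R plus any change common to both arms, and the lavage arm by the common change alone. The difference is R = 3.2 − T. It equals 3.2 only if T = 0. If resection accounts for 75% it is 2.4 degrees; if 50%, 1.6 degrees.

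**3. SD of a change.** With SD 3.8 at both visits, SD of change = 3.8 × √(2(1 − r)): 4.50 at r = 0.3, 3.80 at r = 0.5, 2.94 at r = 0.7. Level and change SDs agree only at r = 0.5. Power falls below that correlation and rises above it.

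**4. Power of the planned change-score t-test** (37 per arm, two-sided 0.0167):

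| Between-arm difference | r = 0.3 | r = 0.5 | r = 0.7 |
|---|---|---|---|
| 3.2 degrees | 73% | 88% | 99% |
| 2.4 degrees | 44% | 61% | 85% |
| 1.6 degrees | 19% | 27% | 46% |

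**5. Power if 12-month rotation is adjusted for baseline.** Residual SD = 3.8 × √(1 − r²): 3.62, 3.29 and 2.71. One df is lost (71), which makes no visible difference.

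| Between-arm difference | r = 0.3 | r = 0.5 | r = 0.7 |
|---|---|---|---|
| 3.2 degrees | 91% | 96% | 99.5% |
| 2.4 degrees | 65% | 75% | 91% |
| 1.6 degrees | 30% | 37% | 54% |

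At r = 0 the residual SD is 3.8, so power at 3.2 degrees is about 87.6% at worst.

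**6. Confidence interval.** At SD 3.8 the half-width matching alpha 0.0167 is 2.45 × 3.8 × √(2/37) = 2.2 degrees.

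**The case against.** **The power is conditional on an alternative, and that alternative is defensible.** The plan says only that 3.2 degrees would be detected with 87% power, which reproduces. Table 1, from the cadaver study, gives some support for a small tear effect: contact area goes from 105 to 98 mm² with a horizontal cut, against 64 and 48 mm² after resection of one or both leaves. This is fair, and it is why the figure is unsupported rather than wrong. But those data concern contact area in cut cadaver knees, not rotation during gait, and the protocol still calls the split unknown.

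**The intact group may be loose wording.** The same paragraph describes the controls as knees without meniscectomy. That may explain the label, but the effect size still comes from healthy knees.

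**The SD point has no direction.** This stands. It calls for a stated assumption and does not demonstrate a shortfall.

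**The flexion moment.** A reader might infer the same fault there. The documents do not settle it: the 0.35 is called an SD of the flexion moment, but it follows a sentence about detecting a change and equals the adduction moment's SD of a difference. It needs clarifying.

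**What a null result would show.** A reader might infer that effects below about 2.9 degrees (the difference with 80% power at SD 3.8) could not be excluded. That confuses a detectable difference with a confidence limit: with a half-width of 2.2 degrees, an observed difference of 0 would exclude 2.9. Nor do the figures support saying that moderate effects would usually be missed, since 2.4 degrees is detected 61% of the time at r = 0.5. No passage sets a rule that treats a null rotation result as proof of no effect.

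**Sample size.** Aim 1 sets it, so no patient number changes. This stands.

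**Conclusion.** The point holds in a limited form. The 87% is the correct power for a 3.2-degree between-arm difference with SD 3.8, but nothing in the documents supports those values for the planned comparison. It would apply if the tear contributed none of the 3.2 degrees and r were about 0.5.

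The effect size is the stronger half: any contribution of the tear in the same direction makes the resection effect smaller than 3.2 degrees. At r = 0.5, power falls to 61% if resection accounts for three quarters of the gap and 27% if it accounts for half. The SD half can move power either way.

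A reader might go further and infer a calculation error or a demonstrably underpowered Aim 2. Neither follows: the figure reproduces, and power at 2.4 degrees alone ranges from 44% to 85% over the correlations shown. No single corrected figure can be given.

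The ranges assume equal SDs at both visits, 37 analysed per arm and two-sided testing. They leave out the debridement of unstable flaps regardless of arm, which under intent-to-treat could shrink the contrast further; its frequency is not given.

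**What to change.** 1. In the Aim 2 power paragraph, name the comparator as the lavage group with the torn meniscus retained. State that 87% assumes the tear causes none of the 3.2 degrees and that r is about 0.5.
2. Print power over effect and correlation together, labelled as assumptions, as in the first table above.
3. Analyse 12-month rotation by a linear model with treatment arm and preoperative rotation. The baseline is already collected. This replaces the plain t-test, makes a level SD the right input, and gives the second table.
4. State whether the flexion-moment SD of 0.35 is that of a level or of a change.
5. State that a non-significant rotation result will be interpreted from the confidence interval for the between-arm difference.

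Cost: changes to the analysis text and a stated power that is conditional and less favourable. No extra patients, visits or measurements.
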